9.3 Interim Analyses of Primary Endpoint

Interim analysis of the study will be performed for all semi-annual DMC meetings beginning when approximately 25% of planned full information (126 events) has occurred. Table 1 gives the expected timing of the analyses and the expected number of events under the alternative at each interim analysis. Because of delays in initiation of accrual and delays in data submission and processing, it is likely the actual analysis time will be 6-12 months later.

The study will be monitored for early stopping in favor of either the alternative hypothesis of superior OS on the clofarabine arm or the null hypothesis of inferior OS on the clofarabine arm using the repeated confidence interval (RCI) methodology similar to that described by Jennison and Turnbull (124). At each interim analysis, a two-sided 95% RCI on the log hazard ratio

(clofarabine/standard) will be computed, using the partial likelihood estimate and their truncated O'Brien-Fleming critical points listed in Table 1. The partial likelihood estimate of log hazard ratio and its robust variance estimator will be obtained using the weighted analysis described in Section 9.2. Since we do not want to stop the trial and declare the inferiority or superiority of clofarabine unless the results are convincing, a hazard ratio of 1 is pre-specified. If at any of the interim analyses, the 95% confidence interval of the log hazard ratio lies entirely below $\log(1)$, we may consider stopping the trial for the superiority of clofarabine; if the 95% confidence interval lies entirely above $\log(1)$, the study may need to be stopped due to the inferiority of clofarabine.

Table 1: The Interim Analyses for the Primary OS Comparison

Real Time (Years)	Information Time	Events Under the alternative	Truncated O-F critical points
2.2	0.25	127	3.2905
2.7	0.34	175	3.2905
3.2	0.44	224	3.2905
3.7	0.54	274	2.9491
4.2	0.64	325	2.6418
4.7	0.74	377	2.4402
5.2	0.85	429	2.2623
5.7	0.92	465	2.1928
7.0	1.00	507	2.0974

9.4 Secondary Objectives

As a secondary objectives of this trial, we will evaluate the 30-day mortality rate (all-cause mortality within 30 days of first dose) of clofarabine in comparison with standard treatment (daunorubicin & cytosine arabinoside) in newly diagnosed AML patients age > 60 years. Based on the results from E3999, we assume the 30-day mortality of standard treatment is 10%. With 747 patients in total, we will have 80% power, at the one-sided 0.0125 significance level, to detect a 6% reduction in the 30-day mortality rate in the clofarabine arm using Fisher's exact test.

Rev. Add10
Rev. 2/12

In this trial, we will also compare the induction complete response (CR) rates between the clofarabine arm and the standard treatment arm. Based on the results from E3999, we assume the CR rate of standard treatment is about 40%. The study team would consider clofarabine to be acceptable if the CR rate is no more than 10% less than the standard treatment. A non-inferiority test was used for this endpoint. Our null hypothesis is that the difference in the CR rates between the standard treatment arm and the clofarabine arm (CR rate of standard treatment – CR rate of clofarabine) is more than 10% and the alternative is that the difference of CR rates between the standard treatment arm and the clofarabine arm (CR rate of standard treatment – CR rate of clofarabine) is less than -1%. With 747 patients in total, the study will have 85% power to reject the null hypothesis of inferiority of clofarabine at the one-sided significance level of 0.025, adjusting for the sequential monitoring described below. At the

end of the study, the 95% confidence interval on the difference in the CR rates (CR rate of standard treatment – CR rate of clofarabine) will be computed based on the normal approximation to the difference of two independent binomial proportions. If the 95% confidence interval lies entirely below 0.1, the non-inferiority of clofarabine in CR rate will be accepted. If the 95% confidence interval lies entirely below 0, then clofarabine is superior to the standard treatment in CR rate.

Rev. 2/12

The induction CR rates will be monitored to allow for early stopping in favor of inferiority using the repeated confidence interval methodology described by Jennison and Turnbull (123). Interim analyses will be conducted for induction CR rates when induction response data is available on 25%, 45%, 65%, 85% and 100% of patients. At each interim analysis, the two-sided 95% repeated confidence interval on the difference of CR rate (CR rate of standard treatment – CR rate of clofarabine) will be computed. This repeated confidence interval uses the critical value from a truncated O'Brien-Fleming error spending rate function with an overall one-sided 2.5% error rate. If the confidence interval lies entirely above 0, the induction randomization may need to be stopped due to the inferiority of clofarabine and subsequent patients will directly be assigned to standard treatment arm.

Another objective of this trial is to determine the effect of decitabine on disease free survival (DFS) as a maintenance therapy in comparison with observation. DFS is defined as the time from the second randomization to relapse or death without relapse. If 25% of patients who do not receive allogeneic transplant go through the second randomization, there will be 172 patients = randomized to either the decitabine arm or the observation arm.

We assume that the long-term cure rate for the observation arm is 10% and the median DFS in the non-cured group is 7 months. The study will have 90% power to detect approximately a 36% reduction in the DFS hazard rate in the decitabine maintenance therapy arm. This power calculation is based on a one-sided log-rank test at the significance level of 0.1 and assumes 5 years of accrual and 2 years of follow-up after the completion of the accrual. The number of DFS events needed is 140. The primary analysis of DFS will be an intention-to-treat analysis and will use a one-sided log rank test stratified on the induction and consolidation therapy and on patient age and cytogenetics.

Another secondary objective of this study is to evaluate the impact of consolidation with non-ablative conditioning and allogeneic hematopoietic stem cell transplantation with an HLA-identical sibling on overall survival in patients who achieve a 'morphologic leukemia-free state'.

The intention-to-treat approach will be used in this analysis. Patients with donors who choose not to have AlloSCT (or are unable due to insurance issues) need to be included in the AlloSCT arm for analysis. Assuming that 50% of patients receiving chemotherapy in induction and consolidation achieve a 'morphologic leukemia-free state' and 25% of those patients have a donor, 94 patients from the allogeneic transplant arm and 280 patients from the chemotherapy arms will be available for this OS comparison.

For the chemotherapy arms, we assume that the long-term cure rate will be 10% and median survival among the non-cured group will be about 9 months. The

study will have 82% power to detect approximately a 32% reduction in the OS hazard rate in the allogenic transplant arm using one-sided log-rank test at the significance level of 0.025. This power calculation assumes 5 years of accrual and 2 years of follow-up after the completion of accrual. Full information needed is 292 deaths. The analysis of this secondary objective will use a one-sided log rank test stratified on age, therapy-related AML, the presence of AHD at the time of diagnosis of AML, and the induction therapy they received.

Rev. Add10

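### The final CR-rate interval leaves out the randomisation strata; it is valid, but slightly conservative if those strata predict remission

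*Combined protocol and SAP*

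**What the plan says.** Sections 4.2.5 and 9.1 stratify the induction randomisation by age (60-69 against 70 and over), therapy-related AML and AHD, which makes at most eight cells.

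Section 9.4 plans a non-inferiority comparison of induction CR rates. It considers clofarabine "acceptable if the CR rate is no more than 10% less than the standard treatment". The final 95% interval for standard minus clofarabine is "computed based on the normal approximation to the difference of two independent binomial proportions". The rule is: "If the 95% confidence interval lies entirely below 0.1, the non-inferiority of clofarabine in CR rate will be accepted". The same interval, if entirely below 0, establishes superiority. On power: "With 747 patients in total, the study will have 85% power to reject the null hypothesis of inferiority of clofarabine". That figure is for a one-sided 0.025 test and is said to allow for the interim looks.

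Other comparisons do use strata. The overall survival interval in Section 9.2 uses the three Step 1 factors. The donor comparison in Section 9.4 uses them plus induction therapy. The disease-free survival test in Section 9.4 uses the factors of its own, second randomisation: it is "stratified on the induction and consolidation therapy and on patient age and cytogenetics". No stratified comparison of CR between the arms is described in Sections 9.1 or 9.4.

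**The concern.** Balancing the arms within strata removes part of the chance variation in the observed CR difference, namely the part that comes from unequal stratum mix. The two-binomial variance still counts that part. Where the strata predict CR, the standard error is therefore somewhat larger than the true sampling variation, and the upper limit sits slightly further from zero than it needs to.

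This interval alone decides CR non-inferiority and superiority, and comparative CR rates are a named secondary objective (Section 2.2.1). What is at stake is a little precision against a 10-point margin. The direction is towards caution, so a false claim of non-inferiority does not become more likely.

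**Working it through.** **Inputs from Section 9.4:** total 747; standard-arm CR rate 40%; alternative difference -1 point, so 41% on clofarabine; margin 10 points; one-sided 0.025. **Assumed:** 1:1 allocation, hence 373.5 per arm. The ratio is not stated for Step 1, but Section 9.8 assumes equal numbers per induction arm.

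**1. The plan's own figure.**

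SE = sqrt[(0.40 × 0.60 + 0.41 × 0.59) / 373.5] = sqrt(0.4819 / 373.5) = 0.0359.

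95% half-width = 1.96 × 0.0359 = 7.04 points.

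Power = Φ(0.11 / 0.0359 − c), where 0.11 is the margin plus the 1-point advantage.

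- c = 1.960 (fixed sample): 86.5%.
- c = 2.051: 84.4%. This is the simulated final critical value for an O'Brien-Fleming-type spending function at 25, 45, 65, 85 and 100% of the data, truncated at 3.2905 (the cap shown in Table 1 of Section 9.3).

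The two values bracket the stated 85%. The planned size matches the unstratified method.

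**2. Effect of using the strata.** Let s be the between-stratum standard deviation of the CR rate, taken as equal in both arms. Each arm's variance p(1 − p) becomes p(1 − p) − s². The documents give neither stratum CR rates nor stratum sizes, so s is varied:

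| s (assumed) | Half-width (points) | Narrower by | Power, c = 1.960 | Power, c = 2.051 |
|---|---|---|---|---|
| 0 | 7.04 | 0% | 86.5% | 84.4% |
| 0.03 | 7.03 | 0.2% | 86.6% | 84.5% |
| 0.05 | 7.00 | 0.5% | 86.8% | 84.8% |
| 0.08 | 6.95 | 1.3% | 87.4% | 85.4% |
| 0.10 | 6.89 | 2.1% | 87.9% | 85.9% |
| 0.15 | 6.70 | 4.8% | 89.5% | 87.8% |

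The row for 0.15 is an extreme, shown only to bound the effect.

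**3. Simulation.** Stratified 1:1 randomisation over eight cells, 200,000 replicates, with assumed prevalences of 50% (older age), 10% (therapy-related AML) and 30% (AHD).

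- Each factor lowers CR by 10 points (s = 0.074). At the margin, the true standard deviation of the unadjusted difference was 0.0343 against a mean estimated standard error of 0.0347, about 1% too large. One-sided type I error was 2.3% unstratified and 2.4% with Mantel-Haenszel weights. Power was 86.8% and 87.3%.
- No factor predicts CR. Type I error was 2.4% for both methods, and power was 86.5% for both.

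**4. Accrual actually reached.** Section 9.5 reports 727 patients when Step 1 accrual was suspended. SE = sqrt(0.4819 / 363.5) = 0.0364, the half-width is 7.14 points, and power is 85.6% (c = 1.960) or 83.4% (c = 2.051). The shortfall of 20 patients costs about 1 point of power, the same order as the gain in step 2.

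**The case against.** The strongest reply is that nothing in the plan is wrong. An unstratified risk-difference interval after stratified randomisation is valid, it holds its error rate, and the stated power was set for it. That stands. A reader might infer that the interval is mis-sized in a harmful direction or that the 85% is unsound; the calculation supports neither.

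A reader might also take it as established that the three factors predict CR in this population. The documents do not show this. Section 1 contrasts CR in older patients with CR in younger adults, who are outside this trial. Section 1.6.5 links therapy-related AML to worse survival, not to CR. The nearest figure, in Section 1.1.2, is for single-agent clofarabine in patients aged 65 or over who were considered unsuitable for chemotherapy: CR 44% above age 70 and 48% overall. If 30% to 70% of them were over 70 (assumed), the remainder had 49.7% to 57.3%, and s for age alone is about 0.03 to 0.06. That is less than a 1% narrowing. The size is therefore conditional, and it may be zero.

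Nor is CR the only comparison left unstratified: 30-day mortality uses Fisher's exact test (Section 9.4). The plan can be read as stratifying its time-to-event tests and leaving these binary ones plain. That weakens a charge of inconsistency but does not remove the gain in precision.

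Mantel-Haenszel weighting can differ from the overall difference if the effect varies by stratum. With near-equal arms inside each stratum, however, the weights are almost proportional to stratum size, so the target barely moves.

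Finally, CR is secondary and does not gate the survival or mortality tests (Section 9.1), and a switch of estimator after results are known would cost credibility. Both points stand. The second determines which analysis should lead.

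**Conclusion.** The point holds as a small, free improvement. The planned interval is valid and no stated figure is wrong. If the strata predict CR, it is conservative by about 0 to 2% of its width for assumed between-stratum standard deviations of 0 to 0.10, equivalent to about 0 to 1.5 points of non-inferiority power. If they do not, nothing is lost. The size rests on that assumed range, on 1:1 allocation and on the Section 9.4 design rates.

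A reader might infer that the interim repeated intervals for CR should change as well. Section 9.5 does not support spending effort there. Step 1 accrual stopped at 727 of 747, so by accrual the looks at 25% to 85% are past. Any patients added for the maintenance question would enter already in remission and could not inform this comparison.

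**What to change.** In Section 9.4, for the final CR analysis, specify a Mantel-Haenszel (or stratified score) risk difference, standard minus clofarabine, with its 95% interval over the Step 1 strata of age, therapy-related AML and AHD. Judge it against the same 0.1 margin, and against 0 for superiority. Keep the two-binomial interval as a sensitivity analysis.

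If CR results by arm have already been seen, reverse the roles: leave the pre-specified unstratified interval as the main analysis and label the stratified one supportive. State in the text which case applies. Leave the interim repeated intervals as written.

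The cost is a sentence or two of analysis-plan wording. The factors are recorded at randomisation, so no new data, patients or follow-up are needed.

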3.2.8 Maintenance Criteria, Step 3 for Arms E and F

3.2.8.1 Maintenance should commence within 60 days of recovery of peripheral blood counts after Consolidation Cycle 2. Patients must begin Consolidation Cycle 2 within 60 days of recovery to be eligible for further therapy.

3.2.8.2 Patients must have maintained peripheral blood evidence of a remission as defined in Section [6](#) and must have a CR or CRi, confirmed on restaging BM aspirate and biopsy and cytogenetic analysis.

3.2.8.3 Patients must have an ECOG performance status of 0 -2.

3.2.8.4 Patients must have resolved any serious infectious complications related to Consolidation Cycle 2.

3.2.8.5 Any significant medical complications related to Consolidation Cycle 2 must have resolved.

3.2.8.6 Patients must have a total serum bilirubin \leq 1.5 x ULN and a serum creatinine \leq grade 1. The values must be obtained within 48 hours prior to randomization.

NOTE: If total bilirubin is 2-3 mg/dL, but direct bilirubin is normal, then the patient will be considered eligible.

3.2.8.7 The ANC must be $>$ 1000 mm³ and the platelet count $>$ 75,000 mm³ prior to starting every cycle of treatment with decitabine. Decitabine may be delayed for up to 4 weeks between cycles (i.e. may be administered as infrequently as q8 weeks) while waiting for counts to recover.

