6.5.3 Flow Cytometry of BM Aspirate

Rev. 2/12 6.5.3.1 If one or more unique leukemia-associated immunophenotypes (LAIP) were identified at diagnosis, minimal residual disease (MRD) levels will be analyzed by multiparameter flow cytometry.

Rev. 2/12 6.5.3.2 Immunologic MRD must be below the level of detection (< 0.001) to qualify for "Leukemia-Free State".

Rev. 2/12 6.5.3.3 Any detectable immunologic MRD levels will be quantified and retrospectively correlated with relapse-free and overall survival.

6.5.4 Extramedullary leukemia must not be present.

6.5.5 If indeterminant, the BM Aspirate & biopsy should be repeated 1 week later.

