10.1.1 Sample Collection and Submission Schedule

Bone marrow, peripheral blood, and smears **must** be submitted at the following time points (**Mandatory Submissions**):

- Pre-Registration
- Notification to the submitting institution:
The ECOG-ACRIN Leukemia Translational Studies Laboratory will notify the submitting institution of the results of the centralized immunophenotyping within 4-6 hours of receipt of the samples.

Rev. 2/12

Rev. 12/13

- Time of Outcome Following Induction – Prior to Consolidation (at time of response assessment or off-study, whichever occurs first)
- End of Consolidation (Prior to 2nd Randomization - Step 3)
- Relapse

Rev. 12/13

Bone marrow and peripheral blood will also be used for the optional correlative studies per patient consent.

Peripheral blood and buccal rinse [preferred] or swabs (baseline only) are to be submitted at the above time points for banking per patient consent.

Rev. 2/12

Samples are to be shipped on the day they are drawn. If this is not possible, call the LTS.

If you have questions, contact the LTS at [contact].

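### The maintenance DFS test adjusts for neither CR/CRi nor pre-randomisation MRD; covariate adjustment could add power (about 0.3 to 8 points, by assumption), nearly all from MRD

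*Combined protocol and SAP*

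**What the plan says.** **The test.** Section 9.4 makes the primary DFS analysis intention-to-treat and says it "will use a one-sided log rank test stratified on the induction and consolidation therapy and on patient age and cytogenetics". These are the Step 3 stratification factors of section 4.4.5.2. Section 9.5 keeps a one-sided log-rank test and names no covariates.

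**The design.** Power is "based on a one-sided log-rank test at the significance level of 0.1". "The study will have 90% power to detect approximately a 36% reduction in the DFS hazard rate in the decitabine maintenance therapy arm", and "The number of DFS events needed is 140". Section 9.5 replaces this with 125 events (hazard ratio 0.63, level 0.10) if the study reopens, or 90 events (hazard ratio 0.64, level 0.15) if it closes. The choice depends on conditional power above 0.7.

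**CR versus CRi.** Under section 3.2.8.2, patients entering Step 3 "must have a CR or CRi, confirmed on restaging BM aspirate and biopsy and cytogenetic analysis".

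**MRD.** Section 10.1.1 lists marrow for the central laboratory as a mandatory submission at "End of Consolidation (Prior to 2nd Randomization - Step 3"), and the table in section 7.3 agrees. Section 6.5.3, under Leukemia Free State, provides for flow MRD only where a LAIP was found at diagnosis. It adds: "Any detectable immunologic MRD levels will be quantified and retrospectively correlated with relapse-free and overall survival". No section says that MRD is reported at the end-of-consolidation time point.

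**The concern.** DFS after the second randomisation counts relapse or death, and remission quality at entry plausibly predicts it. When a baseline factor predicts outcome and the test ignores it, the hazard ratio being tested is pulled toward 1 and power falls. Under the null, the test without the factor and a pre-specified adjusted test are both valid, so this is a question of efficiency and not of bias.

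Efficiency matters here because maintenance is the randomised question that section 9.5 keeps open after Step 1 accrual was suspended. At that point 120 of the 172 planned patients had been randomised. The event target falls from 140 to 125 or 90, and the closed branch relaxes the one-sided level to 0.15. The same comparison feeds the conditional-power decision.

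**Working it through.** **1. The plan's own figures.** Inputs are from sections 9.4 and 9.5, with 1:1 allocation (86 per arm, section 9.8).

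Schoenfeld: power = Φ(|ln HR|·√d / 2 − z).
- 140 events, HR 0.64, z = 1.2816: 0.4463 × 11.832 / 2 = 2.640; 2.640 − 1.2816 = 1.359; power 91.3%. The Freedman form gives 90.6%.
- 125 events, HR 0.63: 0.4620 × 11.180 / 2 = 2.583; power 90.3%.
- 90 events, HR 0.64, level 0.15 (z = 1.0364): 0.4463 × 9.487 / 2 = 2.117; power 86.0% (Freedman 85.2%).

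Events: with S0(t) = 0.1 + 0.9·exp(−t·ln2/7), S1 = S0^0.64, and 60 months of accrual plus 24 of follow-up, event probabilities average 0.8860 and 0.7516. Then 86 × 0.8860 + 86 × 0.7516 = 76.2 + 64.6 = 140.8 events.

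The stated powers and the 140 events reproduce.

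**2. What adjustment would add.** Trials were simulated from the same cure model (5,000 to 6,000 per scenario, Monte Carlo standard error about 0.5 point), with all tests applied to the same simulated trials. The comparator is the planned log-rank in 2 × 2 × 2 = 8 strata. The alternative is a Cox model in those 8 strata with covariates for CRi and MRD, plus an indicator for unknown MRD. The last column instead adds both factors as extra log-rank strata: 8 × 2 × 2 = 32 cells, or 8 × 2 × 3 = 48 when some MRD is unknown.

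Assumed, because the documents give no values: prevalence and hazard ratio of CRi and of MRD positivity, the fraction with MRD unknown, and hazard ratios of 1.2, 1.6 and 1.2 for age, cytogenetics and induction arm.

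| CRi (%, HR); MRD+ (%, HR); MRD unknown | Decitabine HR | Planned % | Cox % | Gain | Extra strata % |
|---|---|---|---|---|---|
| No effect: 20, 1; 30, 1; 0% | 0.64 | 88.7 | 88.6 | −0.1 | 83.0 |
| Weak: 15, 1.3; 20, 1.5; 20% | 0.635 | 88.8 | 89.1 | +0.3 | 81.7 |
| Weak: 20, 1.3; 30, 1.5; 0% | 0.64 | 88.0 | 88.5 | +0.5 | 82.3 |
| CRi only: 20, 1.5; 30, 1; 0% | 0.64 | 87.4 | 87.9 | +0.5 | 81.6 |
| Moderate: 20, 1.5; 30, 2.0; 20% | 0.605 | 90.5 | 92.6 | +2.1 | 84.5 |
| Moderate: same; 20% | 0.64 | 84.5 | 87.0 | +2.5 | 77.2 |
| Moderate: same; 0% | 0.64 | 85.0 | 88.5 | +3.5 | 80.5 |
| 20, 1.5; 30, 2.5; 20% | 0.64 | 83.2 | 87.0 | +3.8 | 77.4 |
| 20, 1.5; 30, 2.5; 0% | 0.64 | 83.5 | 88.0 | +4.5 | 81.7 |
| Strong: 25, 1.8; 35, 3.0; 20% | 0.57 | 90.1 | 94.9 | +4.8 | 87.8 |
| Strong: same; 0% | 0.64 | 79.4 | 87.3 | +7.9 | 79.3 |
| Closed branch (120 patients, about 90 events, level 0.15), moderate; 20% | 0.64 | 79.5 | 81.5 | +2.0 | 70.0 |

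Rows at 0.64 treat the plan's hazard ratio as conditional on CRi and MRD. Rows at 0.605 and 0.57 set the effect so that the planned test itself has about 90% power. The no-effect row is below 91.3% partly because the formulas take no account of splitting patients over eight cells.

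**3. Checks.** Under the null at nominal 10%, rejection was 9.0% (planned) and 9.4% (Cox). Letting MRD correlate with cytogenetics left the moderate gain at +2.2 (84.8% to 87.0%).

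**4. Scale in events.** Events are proportional to (z_α + z_power)². For 90.5% to 92.6% the ratio is (1.2816 + 1.4466)² / (1.2816 + 1.3106)² = 7.443 / 6.720 = 1.108, or about 13 events on 125.

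**The case against.** The strongest reply is that nothing here is an error: the power statements reproduce, testing within the randomisation strata is conventional, and the endpoint is secondary. That stands. Four further points deserve an answer.

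- **MRD availability.** A reader might infer from sections 6.5.3 and 10.1.1 that every patient's MRD is known at Step 3. The documents do not support that. The sample is mandatory, but the assay needs a diagnostic LAIP in an unstated proportion of patients. Section 5.1.6 treats flow in the post-induction leukemia-free state as optional, and the only stated laboratory turnaround is for pre-registration. A sample drawn before randomisation is still a valid baseline covariate if read later, blind to arm and outcome.
- **Prognostic value.** Section 6.5.3 plans a retrospective correlation. It does not assert that MRD predicts relapse.
- **CRi.** CRi covers platelets above 50 and below the CR threshold of 100 × 10⁹/L, while section 3.2.8.7 requires more than 75,000 before each decitabine cycle. Few randomised patients may be CRi, which fits its small contribution.
- **Timing.** With 120 patients randomised and an interim due, changing the primary test could look data-driven. This is manageable, because section 9.11 limits interim outcome analyses to the study statistician and the data monitoring committee. It does require that others specify the change and that this be documented.

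**Conclusion.** The point holds as a cheap efficiency improvement and not as a correction. The maintenance DFS test leaves out CR/CRi, which is in hand for every eligible patient, and MRD, for which the specimen is already mandatory. Adjustment within the existing strata raises power where the factors are prognostic, makes essentially no difference where they are not, and keeps type I error at its nominal level.

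The size depends on assumption: about 0.3 to 0.5 point (weak), 2 to 3.5 (moderate), up to about 8 (strong), and about 2 in the closed branch under moderate assumptions. Nearly all of it comes from MRD. If MRD proves unavailable at this time point, about half a point remains.

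Two stronger readings are tempting. One is that the trial loses some fixed number of points; no such figure can be derived, because the documents give neither prevalence nor hazard ratio for either factor. The other is that the stated 90% power is wrong; it is not. The effect on the conditional-power decision was not quantified.

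**What to change.** In sections 9.4 and 9.5, before the maintenance interim is examined, and written by staff without access to outcome data:

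- Make the primary DFS test a Cox model stratified on induction/consolidation therapy, age and cytogenetics. Add as covariates CR versus CRi at Step 3, and MRD from the last central marrow drawn before the second randomisation (detectable / not detectable / no LAIP or not assessed).
- State that MRD is read without knowledge of arm or outcome, and confirm with the central laboratory that it is run on this specimen and in what fraction of patients.
- Test the decitabine coefficient one-sided at the stated levels (0.10, or 0.15 in the closed branch), and use the same model for conditional power.
- Keep the stratified log-rank as a sensitivity analysis.
- Do not add the factors as further log-rank strata: in the scenarios above that lost about 0.1 to 9.5 points.

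**Cost.** SAP wording and a merge of laboratory data that section 10.9 already makes due quarterly; no new patients or specimens. The downsides are a not-assessed MRD category, a hazard ratio conditional on the covariates, and the need to document that the change was made blind to outcome.
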